832 As per the UB Human Studies guidance 05212020.docx, the following will be done prior to all participant  
833 visits:

834 During the reminder call the day before a visit:

835 • Participants will be asked to take their temperature; if they don't have a thermometer, they will be  
836 asked whether they feel feverish.

837 • Participants will be asked about the presence of any COVID-19 symptoms including: fever, cough,  
838 shortness of breath, sore throat, muscle aches, headache, new loss of taste or smell, and repeated or  
839 shaking chills (as noted on page 2 of the UB Human Studies Guidance 05212020.docx).

840 • Anyone known to be COVID-19 positive or who exhibits COVID-19 symptoms will be restricted from  
841 enrollment / attending in-person visits until symptom free and at least 14 days since date of diagnosis.  
842 For enrolled participants, remote visits (telemedicine) will be scheduled in the interim as the health of  
843 the participant allows.

844 Before leaving home on the day of a visit

845           • Participants will be asked to take their temperature at home.

846           • Participants will be asked to report any new symptoms on the day of the visit to the project coordinator

847           prior to coming to the clinic/lab.

848           • Participants will be asked to wear a face covering prior to entering the building; if they arrive without a

849           face covering, a mask will be provided.

850           **Revised Visit Scheduling Enhances Social Distancing:**

851           • To support physical distancing and prevent congestion, intake appointment times will be arranged so

852           that no more than 4 participants are present on site at any one time. There is ample space in Diefendorf

853           to assure appropriate physical distancing with up to 8 private office spaces for participant

854           interviews/counseling sessions.

855           • Clinic visits will be scheduled with at least 15 minutes staggering of arrivals and departures of other

856           participants and clinic staff, and allocated duration of visits will be increased by 15 minutes to ensure

857           time for disinfection of hard surfaces at the conclusion of each visit.

858           **Consent Addendum:** A consent addendum will be employed that advises participants of all COVID-

859           related requirements and procedures. See Section 29.0: Process to Document Consent.

860           **Disinfection of Shared Equipment and Spaces:**

861           • Before and after each in-person appointment or use of a shared room or piece of equipment, all hard

862           surfaces such as equipment (including the shared copier), countertops, keyboards, computer mice,

863           office chair arms, and doorknobs will be disinfected with EPA-approved disinfectant wipes or spray.

864           • A disinfecting checklist will be placed on the door of each participant room or shared space; staff will

865           provide the date, time, and staff initials after each disinfection.

866           • Participants will be given a pen to use during their visit that then will then take with them so multiple

867           people aren't using the same pen.

868           **Remote Study Visits:**

869           Study visits will be conducted remotely, rather than in person at UB, under the following circumstances.

870           • If a participant reports COVID-19 symptoms or diagnosis, then remote visits will be scheduled at least

871           until the participant is symptom-free and it has been at least 14 days since the date of diagnosis.

872           • If UB determines that research projects cannot have in-person visits for a period of time (for example,

873           if there were a surge of COVID-19 cases in the area), all appointments will be conducted remotely

874           during that period of time.

875           • Other circumstances in which study staff and the participant agree that one or more remote visits are

876           appropriate in order to ensure uninterrupted smoking-cessation treatment

877           • To enhance compliance with follow-up appointments at which primary outcome measures are

878           collected, these visits may be conducted remotely as well

880           Participants will be instructed regarding the details of remote study visits, including the need for privacy,

881           the methods for delivery and return of study materials, and the technology (Zoom or telephone; REDCap)

882           for completing study visits. Informed consent for remote study visits will be obtained with the aid of the

883           attached *EVarQuit Consent Addendum – COVID-19.docx*.

885           **UPDATE 2020-06-12 - ELIMINATION OF LAB VISITS FOR REMAINING PARTICIPANTS.** As

886           noted above, due to concerns about enrollment, participant burden, and perceived ppt risks, we are

887           eliminating the lab visits for the remaining participants.

888

889           **UPDATE 2020-06-30 – OPTIONAL SALIVA SAMPLE FOR GENETIC ANALYSIS.** Consistent with

890           the administrative supplement submitted to NCI, ITT participants will be asked to provide an optional

891           additional saliva sample for genetic analysis. In brief, 30 minutes after eating, drinking, or smoking,

892 participants who consent to provide a genetics sample will provide a 2 mL saliva sample using an Oragene  
893 kit (DNA Genotek, Inc.).

894 For participants enrolled after approval of the genetics sample, an overview and the consent  
895 addendum (see EVarQuit Genetics Sub-Study - Consent Addendum - onsite - 2020-06-30.docx) will be  
896 presented at Clinic 2 (future participants). Reasons for waiting until Clinic 2 (as opposed to including with  
897 the initial study consent at intake) include: a) Because the major focus of these analyses is to better  
898 understand variability in response to varenicline, and varenicline is first measurable at Clinic 2, we do not  
899 wish to obtain samples from participants who are found ineligible or withdraw prior to Clinic 2, and b)  
900 Providing the consent addendum in close temporal proximity to obtaining the sample, rather than adding  
901 the information to the already lengthy consent form at intake, should enhance participant understanding of  
902 what is required versus optional and improve understanding of the specific issues related to the optional  
903 genetics sample.

904 For participants who have already completed Clinic 2, an overview and the consent addendum will  
905 be presented at their next study visit (see EVarQuit Genetics Sub-Study - Consent Addendum - onsite -  
906 2020-06-30.docx). If the participant has already completed all required study visits, study staff will attempt  
907 to reach the participant by phone and/or email (see EVarQuit Genetics Sub-Study Initial Contact – Phone  
908 and Email Scripts 2020-06-30.docx). No more than two attempts with each method will be made, to avoid  
909 “hounding” the participant. If the participant is reached and expresses interest, or if the participant was not  
910 reached by phone/email, the following will be sent by postal mail:

- 911 - EVarQuit Genetics Sub-Study – Addendum Cover Letter – 2020-06-30.docx
- 912 - EVarQuit Genetics Sub-Study - Consent Addendum - home - 2020-06-30.docx

913 Participants who return written consent to providing the sample will be mailed standard DNA Genotek  
914 Oragene saliva sample kit and pre-paid return mailer. Participants will be remunerated upon receipt of the  
915 sample (see Remuneration).

916  
917 Regarding issues relevant to Section 2 of HRP-399 (WORKSHEET: Additional Requirements for Genetic  
918 Testing (NY State)):

- 919 • Consent will be obtained directly from the participant (no samples taken from deceased individuals).
- 920 • As described in the consent addendum, samples will be stored independent of other participant  
921 information, making it impossible that genetic information would ever be incorporated into the records  
922 of a nonconsenting individual.
- 923 • Consent for banking and additional genetic testing are explicitly obtained in the consent addendum.
- 924 • As explicitly stated in the consent addendum: “If you say yes now, but you change your mind later, it  
925 will not be held against you or affect your participation in EVarQuit. You can always call ([name]  
926 [name]) or email us ([contact]) to say that you have changed your mind, and the DNA  
927 sample will be destroyed.” In such an event, the PI ([name]) will contact [name] at the  
928 University of Toronto to ensure the deidentified sample is destroyed.
- 929 • “Family members of an individual who provided a stored tissue sample will NOT be contacted for  
930 clinical, research, or other purposes without consent from the individual who provided the tissue  
931 sample with respect to the specific family members who will be contacted and the specific purpose of  
932 the contact.” (HRP-399) As of this version of the protocol, we do not anticipate ever contacting family  
933 members of participants and would submit a modification in advance of any such contact.
- 934 • “Information about an individual derived from genetic tests performed on stored human tissue or  
935 information linking an individual with specific results of genetic tests will NOT be released to any  
936 organization or person without the explicit written consent of the individual who donated the stored  
937 tissue to release of the information for the purposes set forth in the written consent document” (HRP-  
938 399).

939     • “DNA samples will be stored for no more than ten years in the absence of genetic testing, if authorized  
 940       in writing by the subject. If genetic testing will be performed on the stored samples or samples will be  
 941       stored for more than 10 years, informed consent will be obtained” (HRP-399).

942

943     10.2 *Describe what data will be collected.*

944       *NOTE: For studies with multiple data collection points or long-term follow up, consider the*  
 945       *addition of a schedule or table in your response.*

946       Response: Measures reflect the aims of the project: evaluating the efficacy of a promising approach to  
 947       smoking cessation (Aim 1, with a focus on abstinence at EOT and 6M), and gaining insight into the  
 948       mechanisms and moderators of treatment effects (Aims 2 and 3; with an emphasis on measures obtained  
 949       between Intake and TQD). Please see the table of assessments and measures in Section 11.1

950

951       10.3     *List any instruments or measurement tools used to collect data (e.g.*  
 952       *questionnaire, interview guide, validated instrument, data collection form).*  
 953       *Include copies of these documents with your submission.*

954

Response:

955       Smoking rate – How many cigarettes did you smoke yesterday?

956       █ Expired-air CO – Biochemical verification obtained with a hand-held carbon monoxide (CO) meter  
 957       (see CRF – e.g. EVQCRFs - Intake - Staff Instruments).

958       █ Cotinine/3-hydroxy-cotinine – Biochemical verification and rate of metabolism – patients will provide  
 959       saliva samples at all Clinic visits as well as follow-up visits, (see App10.3-03).

960       █ Varenicline levels – patients will provide saliva samples at all Clinic visits, EOT and 6 month follow-  
 961       up.

962       █ Validated Questionnaires that assess the following are included in App10.3-04- Questionnaires-2016-  
 963       09-23.docx:

964

- Craving
- Withdrawal
- Subjective effects of smoking
- Nausea
- Treatment expectancies

969

970       █ The urine collection and drug testing procedure is described in App10.3-05-UrineToxProcedure.

971       Our standard side effects assessment (e.g., [name] et al., 2012; Lerman et al., 2015) has been updated to  
 972       include the CSSRS and is included on the CRFs for intake.

973

2020-04: App - COVID-19 Quitting Questions\_v3.5 - EVarQuit 2020-04-20.docx

974

2020-05-19: App – COVID-19 Structured Interview-EVarQuit 2020-05-19.docx

975     10.4 *Describe any source records that will be used to collect data about subjects (e.g. school records,  
 976       electronic medical records).*

977

Response: N/A, no external records will be used to collect data about subjects.

978

N/A. We will not obtain external source records.

979 10.5 *Indicate whether or not **individual** subject results, such as results of investigational diagnostic tests,*  
 980 *genetic tests, or incidental findings will be shared with subjects or others (e.g., the subject's primary*  
 981 *care physician) and if so, describe how these will be shared.*

982 Response: Individual subject results will not be shared with participants or others.

984 10.6 *Indicate whether or not **study** results will be shared with subjects or others, and if so, describe how*  
 985 *these will be shared.*

986 Response: We will maintain a list of participants who would like to be notified of study results and will  
 987 provide those participants with brief summaries of project results in short newsletters in the Fall of 2020,  
 988 2022, and 2024. These summaries will be shared via email or post based on participant preferences.

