 683 the post-quit period: increased frequency of payment (from once every two weeks to three times per week)  
 684 and increased amount of payment (from \$1/assessment to \$2/assessment).

685 In order to complete the EMA SWAT, over the course of a one-year period participants (equal  
 686 numbers of male and female, and of Caucasian and African-American) will be randomly assigned to each  
 687 of three conditions in advance of the TQD until we accrue 20 participants in each condition. At the TQD,  
 688 participants in the SWAT will receive a written consent addendum.

689  For the three versions of the addendum, see EvarQuit Addendum – EMA SWAT – 2018-12-06.doc.

690 Participants randomly assigned to the standard condition would simply be informed that it is  
 691 important to continue the EMA over the next four weeks. Participants randomly assigned to the increased  
 692 frequency of payment and increased amount of payment will have the opportunity to accept or decline the  
 693 modified payment plan. If they decline, they will simply continue to participate in EVarQuit, but will be  
 694 not be enrolled in the SWAT.

695 We chose individualized addenda over a single broad consent form because the SWAT will only  
 696 pertain to a subset of EVarQuit participants. We considered explaining all three conditions to SWAT

697 participants, but ultimately decided against it because doing so could cause unnecessary distress to  
 698 participants randomized to the standard condition (who might feel they were 'losing out' even though  
 699 nothing had changed).

700 The results of the SWAT will inform our decision of whether to alter remuneration for subsequent  
 701 participants in the EVarQuit project.

702 *Clinic visits (Weeks -4, -3, -1, 0 [TOD], 2, and 4), randomization, and study medication.* At Clinic  
 703 Visit 1 (Week -4), participants are randomized (within gender) to the extended or standard run-in group,  
 704 complete study measures (see below), receive brief behavioral counseling (see below) and study  
 705 medication (details below), and are instructed to begin the medication the next day. Subsequent study visits  
 706 are similar in process and content. *Randomization.* The study statistician (Co-I [name]) will implement  
 707 and monitor the small-urn randomization (within-gender in urns/blocks of 8 [4 extended run-in, 4 standard  

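### The EMA payment sub-trial drops decliners after randomisation and describes a choice to decline only in the two incentive conditions, so its comparison with standard payment is not protected by randomisation.

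*Combined protocol and SAP*

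**What the plan says.** All of this stands in protocol Section 10.1, under the SWAT on EMA Remuneration.

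- **Randomisation comes first.** Assignment is to each "of three conditions in advance of the TQD until we accrue 20 participants in each condition. At the TQD", and it is then that "participants in the SWAT will receive a written consent addendum". The addendum exists in three versions ("For the three versions of the addendum, see EvarQuit Addendum"); their text is not in the documents.
- **Standard condition.** "Participants randomly assigned to the standard condition would simply be informed that it is" important to carry on with EMA for the next four weeks. No choice is described.
- **Incentive conditions.** Those assigned to increased "frequency of payment and increased amount of payment will have the opportunity to accept or decline the" new terms. The text then says of the "modified payment plan. If they decline, they will simply continue to participate in EVarQuit, but will be" left out of the sub-study; the sentence ends with the words "not be enrolled in the SWAT".
- **Use.** "The results of the SWAT will inform our decision of whether to alter remuneration for subsequent" participants.

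Section 17 (Data Management and Analysis) does not mention the SWAT. No analysis set, test, expected decline rate or handling of decliners is given for it. The parent trial, by contrast, does define an intent-to-treat sample (Section 10.1, on clinic visits and randomisation).

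**The concern.** Randomisation makes the three groups comparable at the moment of assignment. Here people can leave two of the groups after that moment, by their own choice, and no matching exit is described for the third. The people left in the incentive conditions are those willing to take on new payment terms, while the standard condition keeps everyone assigned to it. If willingness is related to EMA completion, the groups would differ even if the incentives did nothing.

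At stake is a payment decision for later participants. The protocol gives its reason for the SWAT as adherence that is lowest in the four weeks after quitting. A selection effect taken for an incentive effect could lead the trial to spend more per assessment, or pay more often, for little return.

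**Working it through.** **1. Order of events.** Random assignment precedes the TQD. Addendum and offer come at the TQD. Acceptance or refusal in the incentive conditions follows, and refusal means leaving the SWAT. The exclusion is therefore after randomisation and is described for two of three conditions.

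**2. The plan's own figure.** The only number is 20 per condition, 60 in total. It cannot be reproduced, because no alpha, power, effect size or standard deviation is stated for the SWAT. For scale, with 20 per group, two-sided alpha 0.05, 80% power and a normal approximation, the detectable difference is (1.960 + 0.842) × √(2/20) = 0.89 SD. If the SD of completion is 20 points (assumed), that is about 18 points.

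**3. Size of the bias.** Let p be the share declining, and A and D the mean completion of accepters and decliners under the same payment. Everyone assigned averages (1 − p)A + pD, while accepters alone average A. With no true incentive effect:

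bias = A − [(1 − p)A + pD] = p × (A − D).

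If decliners are replaced, an incentive condition needs 20 / (1 − p) people randomised, rounded up, to reach 20 accepters; the standard condition needs 20. All values of p and A − D below are assumptions.

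| Declining (p) | Randomised per incentive condition | Bias, A − D = 10 | 20 | 30 | 40 | −20 |
|---|---|---|---|---|---|---|
| 2% | 21 | 0.2 | 0.4 | 0.6 | 0.8 | −0.4 |
| 5% | 22 | 0.5 | 1.0 | 1.5 | 2.0 | −1.0 |
| 10% | 23 | 1.0 | 2.0 | 3.0 | 4.0 | −2.0 |
| 20% | 25 | 2.0 | 4.0 | 6.0 | 8.0 | −4.0 |

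Bias is in percentage points; positive values favour the incentives. With no decliners, or with A = D, it is zero.

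**4. Effect on false positives.** The plan names no test, so assume a two-sided normal test at 0.05. With SD 20, the standard error is 20 × √(2/20) = 6.32 points. For a bias b, the type I error is 1 − Φ(1.96 − b/6.32) + Φ(−1.96 − b/6.32).

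- b = 1 (5% declining, gap 20): 0.053.
- b = 2 (10%, gap 20): 0.062.
- b = 6 (20%, gap 30): 0.158; with SD 30 instead, 0.097.
- b = 8 (20%, gap 40): b/6.32 = 1.26, giving about 0.24.

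**5. With everyone kept.** Analysed as assigned, both sides estimate (1 − p)A + pD when there is no effect. The selection bias is zero and the type I error stays at 0.05.

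**The case against.** **Direction is not documented.** A reader might infer that the comparison is biased toward the incentives. That needs some people to decline, and decliners to be the less adherent ones; the documents say neither. They even suggest a route the other way. Section 25.1 capped total pay at $599 when the SWAT was added, and the 2019-11 retention update in Section 10.1 says pay had been held under the $600 level at which participants must give a Social Security number. Doubling pay for four weeks of 35 assessments adds up to 35 × 4 × $1 = $140, so the maximum becomes $739. Pay apart from EMA was at most $599 − $315 = $284. Doubled EMA pay would total at most 5 × $35 + 4 × $70 = $455, so a participant attending everything reaches $600 at ($600 − $284) / $455, or about 69% of it. Anyone refusing for that reason would be a good completer, and removing them would bias against the higher-payment condition. This is inference too, but it is enough to leave the sign open.

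**Exclusivity is not certain.** A reader might also infer that refusal is possible only in the incentive conditions. The standard condition has its own version of the consent addendum, whose text is not available, so refusal there cannot be ruled out. What stands is that a choice is described only for the other two.

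**Replacement is inferred.** Accrual to 20 per condition suggests that decliners are replaced, but the text does not say so. The selection problem remains even without replacement.

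**The effect may be small.** The offer is double pay, or the same pay sooner, and few may refuse. At 2% to 5% declining and gaps of 10 to 30 points the bias is 0.2 to 1.5 points, far below the roughly 18 points that the SWAT could detect.

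**Reach is limited.** The result informs the payment decision; the text does not say that it settles it. The SWAT was pending funding, the documents do not say whether it ran, and the 2019-11 and 2020-06 payment texts still give $1 per assessment.

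These points limit direction, size and consequence. They do not supply an analysis rule that keeps decliners in their assigned groups.

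**Conclusion.** The point holds as a differential exclusion after randomisation in an ancillary sub-study. Followed as written, the plan compares accepters with everyone assigned to standard payment, and nothing in Section 17 corrects this. The risk is plausibly toward the incentives, since people who turn down better payment terms may be less engaged with EMA, but direction and size are unknown. The range of roughly 0.2 to 8 points rests wholly on assumed decline rates of 2% to 20% and assumed gaps of 10 to 40 points; zero or a reversed sign is also possible.

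It would be wrong to read this as a threat to the varenicline comparison. Nothing in the documents links the exclusion to Aims 1 to 3, because decliners stay in the parent trial. The importance is low, but the remedy is cheap.

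**What to change.** Add an analysis rule for the SWAT: everyone randomised to a SWAT condition is counted in that condition, decliners included; the comparison is of EMA completion over the four post-quit weeks by assigned condition; and the number declining is reported for each condition. Accrual to 20 should count people assigned, not people accepting. State also whether standard-condition participants can refuse, and treat any who do in the same way.

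No new data collection is needed. Decliners remain in EVarQuit, whose daily EMA runs through Week +4 (Section 10.1, Ecological Momentary Assessment). If the SWAT has already run, the rule can still be applied, provided the assignment log was kept.

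There are two costs. The estimate becomes the effect of offering the payment plan: if decliners gain nothing from it, the effect among accepters is multiplied by (1 − p), that is by 0.98 to 0.80 over the assumed 2% to 20%. For a decision on what to offer later participants, that is the relevant quantity. Second, because decliners are not enrolled in the SWAT, an addendum or IRB line may be needed to confirm that their parent-trial EMA data are used. Obtaining the same consent in all conditions before randomisation would also work, but it would mean describing all three payment plans to everyone, which the protocol chose to avoid.
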